**1.2.3.3 Determine if PRISM-AC improves other key patient-reported outcomes**

**1.2.3.3.1 Outcome Measures:** Anxiety and Depression (measured with Hospital Anxiety and Depression Scale, HADS), symptom burden (Memorial Symptom Assessment Scale, MSAS), hopeful patterns of thought (Hope Scale), Cancer-Specific Quality of Life (PedsQL 3.0 Cancer Module), and Resilience (Connor Davidson Resilience Scale, CDRISC-2) 3-months post-enrollment.

**1.2.3.3.2 Hypotheses:** PRISM recipients will report lower anxiety and depression, lower symptom distress, higher hope, and higher resilience compared to controls.

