**1.2.3.4 Evaluate the impact of PRISM-AC on parent distress.**

**1.2.3.4.1 Outcome Measures:** parent anxiety (Generalized Anxiety Disorder Screener, GAD-7), depression (PHQ-8), and HRQOL (SF-36), 3-months post-enrollment.

**1.2.3.4.2 Hypothesis:** Parents of PRISM-AYAs will report lower anxiety and depression, and better HRQOL compared to parents of AYAs in usual care.

**1.2.3.4.3 Exploratory Outcome:** Family Experience (selected items from Hospital Consumer Assessment of Healthcare Providers and Systems [HCAHPS] survey).

**1.2.3.5** Evaluate the impact of PRISM-AC on family “palliative care activation.”

**1.2.3.5.1 Outcome measures:** (a) AYA- and parent- perceptions of AYA involvement in Decision-Making, measured with the Decision-Making Involvement Scale; (b) medical record documented goals of care conversations; and, (c) medical record documented AYA utilization of formal palliative care and other psychosocial services, hospice, limitation of intervention orders, and other advance care plans.

**1.2.3.5.2 Hypothesis:** PRISM families will demonstrate higher levels of activation compared to usual care.

**1.2.3.6** Explore longitudinal impact of PRISM-AC on above outcomes at 6-, 9-, and 12-months following enrollment.

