## 9.5 Data collection schedule for study staff.

### 9.5.1 For the AYA and caregiver survey schedules for both the run in and RCT, please see

Figures 3A and 3B. Medical record data will be collected at baseline and monthly until the 3-month mark in both the run in and RCT. Additional medical record abstraction will occur for the RCT at 6-, 9, and 12-months. The caregiver to complete the surveys will be designated at enrollment. RA's at each site will prospectively abstract information from the medical record using a study-specific case report form (CRF) adapted from prior studies. This will include: (1) AYA participation in goals of care conversations: dates of documented conversations with medical team regarding prognosis, treatment decisions, and/or goals of care, whether or not AYA was present, and if there is documented active AYA participation. (2) Benchmarks of Palliative Care Utilization: number and frequency of documented psychosocial and palliative care referrals and meetings, hospice referrals, limitation-of-resuscitation orders, completion of advance care planning documents, and end of life details (i.e. location of death, clinical involvement and family support (sibling & financial assessments)). (3) Clinical covariates: the AYA's diagnosis, cancer/tumor-directed treatments, and intensity in the past month, number of and reason for hospital days

(anticipated and unanticipated), prescription psychiatric and/or mood altering medications, prescription opioids and other pain medications, and number of documented palliative care/psychosocial encounters. These variables were selected based on prior evidence that child well-being and family psychosocial needs affect immediate psychosocial outcome metrics (e.g., psychological distress and quality of life).

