**Table 5. Resilience in Pediatric Cancer Assessment (RPCA) Instruments**

Objective	Concept	Instrument(s)	Source
Aim 1 (AYA Outcomes)	HRQOL (Primary Outcome)	PedsQL Generic Core and Cancer Modules (PedsQL) 20,21†‡	AYAs
	Anxiety/ Depression	Hospital Anxiety and Depression Scale (HADS) 22†‡	
	Symptom Burden	Memorial Symptom Assessment Scale (MSAS) 24†‡	
	Hope	Hope Scale 25†	
	Resilience	2-item Connor-Davidson Resilience Scale 	
		10-item Connor-Davidson Resilience Scale 94†	
Aim 2 (Parent Outcomes)	Anxiety	Generalized Anxiety Disorder Screener (GAD-7) 	Caregivers
	Depression	Patient Health Questionnaire (PHQ-8) 	
	HRQOL	Medical Outcomes Study Rand Short-Form 36 29‡	
	Family Experience	Family Experience Survey (HCAHPS) 	
Aim 3 (Activation)	Activation	Decision Making Involvement Scale 31‡	AYAs and Caregivers
		Survey of Caring for Children with Cancer (SCCC) †‡	
		Patient Activation Measure (PAM-13) 120†	
		Benefit Finding 121†	
	Demographic Questionnaire	Demographic information †	AYAs and Caregivers
	COVID-19 Impact	The COVID-19 Impact Questionnaire ‡	AYAs and Caregivers
	Quality of Care Checklist	Quality of Care Checklist †	AYAs

† Included in RPCA for “run-in”

‡ Included in abbreviated RPCA surveys

The full RPCA survey will be administered at baseline and week 12 in the RCT. (**Figure 3**). In order to optimize engagement, patients in both arms of the study will be asked to complete the abbreviated Resilience in Pediatric Cancer Assessment (aRPCA) during the

prospective longitudinal follow-up period (months 6, 9, and 12). The aRPCA will assess only selected outcomes (patient outcomes of HRQOL & symptoms, parent outcomes of HRQOL, and family activation variables), as described below. For those on the non-intervention arm of the study, staff will schedule a “study check-in” visit to coordinate the aRPCA completion and thank families for their continued participation.

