## 11.5 Analysis Plan

**11.5.1 Overview.** The primary statistical analyses will be intention-to-treat to avoid confounding by non-random participant attrition. Demographics, clinical characteristics, and items within the RPCA will be summarized at each time-point using descriptive statistics: frequencies and proportions for categorical variables, means and standard deviations for continuous variables, or median and interquartile range if the distribution is markedly skewed. All analyses will be adjusted for site and patient age, as randomization is stratified by these 2 variables, as well as baseline characteristics clearly imbalanced between groups.

**11.5.2 Primary Outcome.** Our primary outcome is AYA reported HRQOL at 12 weeks. Because the amount of change depends strongly on the initial HRQOL at baseline we will control for baseline HRQOL as a covariate in the regression. Regression models will be used to estimate mean-level differences and 95% confidence

intervals comparing scores in the PRISM intervention to those in usual care. The mean total PedsQL generic core score will be the outcome, and the PRISM intervention the predictor, of interest. A generalization of the two-sample t-test based on a contrast of the regression model will examine if there is an increase in PedsQL scores from baseline for PRISM versus usual care at the primary time point of interest, 3 months following enrollment. The same analysis will be undertaken for the domain subscales of PedsQL (physical and psychosocial), the cancer-specific module, and secondary outcomes included in AYA surveys. Subgroup analyses will explore whether the effect of the intervention is modified by medical covariates, symptom distress, and/or concurrent parent distress. Response type (survey, interview, or parent proxy) will be included in sensitivity analyses and data reported separately if indicated. The rationale for these subgroup analyses is grounded in prior findings suggesting symptoms and parent wellbeing are associated with patient HRQOL.

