### 11.5.3 Secondary Outcomes

**11.5.3.1** The goal for parent outcomes is to evaluate the effect of the intervention on *parent psychological distress* and HRQOL. Mean total scores from each parent instrument at 12 weeks will be the secondary outcomes of interest. We will model distress and HRQOL separately and follow a similar approach to the analyses for continuous outcome measures in Aim 1. As sex and baseline patient HRQOL may be predictors of these outcomes, each will be included if imbalanced between arms.

**11.5.3.2** To compare patient and caregiver *activation*, we will measure patterns in multiple domains: AYA- and parent-reported Decision-Making Involvement Scores, AYA participation in goals of care conversations, and formal palliative care service utilization including documented referrals for hospice and charted decisions to limit resuscitative efforts. For all outcomes, results between trial groups will be compared using analysis of variance with trial group as the factor of interest. We will explore whether change in activation scores are correlated within families and/or modified by parent/child characteristics (sex, psychological distress scores, cancer/tumor-type, among others) using ordinal logistic regression models with cumulative logits, where change activation level is categorized as negative, null, or positive.

**11.5.3.3 Exploratory analyses** will evaluate prospective and longitudinal survey and clinical data beyond month 3 (primary endpoint) at months 6, 9, and 12 of the study. Comparisons between groups will still use an intention to treat approach as described above. Additionally, we will explore the relationship between biomedical variables and patient reported anxiety and depression through a combination of paired and unpaired t-tests, chi-squared (or Fisher's exact) tests, and linear and logistics regression. HRV will be measured in 24-hour increments using both time and frequency domain parameters as established by the international Cardiology task force

guidelines. Means and standard deviations will be compared to published normative data in adolescents.

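### Section 11.5.2 names concurrent parent distress as an effect modifier, and dates none of the others; all modifiers should be fixed at baseline

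*Combined protocol and SAP*

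**What the plan says.** The subgroup sentence in Section 11.5.2 reads: "Subgroup analyses will explore whether the effect of the intervention is modified by medical covariates, symptom distress, and/or concurrent parent distress". Its rationale is "prior findings suggesting symptoms and parent wellbeing are associated with patient HRQOL", which says nothing about timing. For the primary model the same section is explicit about timing: "we will control for baseline HRQOL as a covariate in the regression".

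Two of the three modifiers are also things the trial expects PRISM to change. Section 1.2.3.3.2 states: "PRISM recipients will report lower anxiety and depression, lower symptom distress, higher hope, and higher resilience compared to controls". Section 1.2.3.4.2 states: "Parents of PRISM-AYAs will report lower anxiety and depression, and better HRQOL compared to parents of AYAs in usual care". Section 11.5.3.1 makes the parent scores outcomes in their own right: "Mean total scores from each parent instrument at 12 weeks will be the secondary outcomes of interest".

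On data collection, the text after Table 5 states: "The full RPCA survey will be administered at baseline and week 12 in the RCT". Section 9.5.1 states: "Medical record data will be collected at baseline and monthly until the 3-month mark in both the run in and RCT". So baseline and post-randomization values are planned for all three kinds of modifier. No section says which will be used.

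**The concern.** A subgroup comparison keeps the protection of randomization only if membership is settled before treatment can affect it. If families are grouped by parent distress at 3 months, and PRISM has lowered that distress, the low-distress group contains PRISM families who are there because of PRISM and usual-care families who would have been there anyway. The high-distress group is selected in the mirror-image way. The arms then differ within each group in more than treatment, and whatever part of the effect works through distress is partly removed.

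The same would apply to symptom distress taken at 3 months. It could also apply to some medical covariates: Section 9.5.1 counts palliative care and psychosocial encounters among them, and Section 1.2.3.5 hypothesizes more such activity under PRISM. What is at stake is the reading of the effect-modification results, not the trial's main result.

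**Working it through.** **1. The plan's own figure.** Inputs from Section 11.3.1.1: difference 8.1, SD 17.2, 72 evaluable per arm, 26% attrition; Table 7 gives the 5% error rate, taken here as two-sided. SE = 17.2 × √(2/72) = 2.867; 8.1/2.867 = 2.83; power = Φ(2.83 − 1.96) ≈ 0.81 (0.80 with the t distribution). 144/(1 − 0.26) = 194.6, so 195 randomized. The figures reproduce, and none depends on the subgroup sentence.

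**2. Timing of each modifier.**

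| Modifier | Time point in 11.5.2 | When collected | Could PRISM change it? |
|---|---|---|---|
| Parent distress | *concurrent* | baseline, week 12 | yes, hypothesized (1.2.3.4.2) |
| Symptom distress | none | baseline, week 12 | yes, hypothesized (1.2.3.3.2) |
| Medical covariates | none | baseline, monthly to month 3 | some could (1.2.3.5) |

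**3. Size of the distortion, under assumptions.** Let M be 3-month distress in SD units: mean 0 in usual care, mean −τ under PRISM, normal with SD 1. Let the total effect be 8.1 in everyone, with a share p of it running through M. The slope of HRQOL on M is then −g, with g = p × 8.1/τ. Within a subgroup S the expected difference between arms is

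effect(S) = 8.1 − g × (τ + d), where d = mean M under PRISM minus mean M under usual care, within S.

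For subgroups formed at baseline, d = −τ and the effect is 8.1. If PRISM does not change M, nothing runs through it and the effect is again 8.1.

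Take τ = 0.5, in line with the parent detectable differences in Table 7: GAD-7 1.7/3.4 = 0.50; PHQ-8 1.8/3.7 = 0.49.

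*Median split* (cut at −0.25). Low half: usual care −0.387/0.401 = −0.964; PRISM −0.5 − 0.387/0.599 = −1.146; so d = −0.182 and τ + d = 0.318. The upper half is the same by symmetry.

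| p | g | Effect in both halves |
|---|---|---|
| 25% | 4.05 | 8.1 − 4.05 × 0.318 = 6.8 |
| 50% | 8.10 | 8.1 − 8.10 × 0.318 = 5.5 |
| 75% | 12.15 | 8.1 − 12.15 × 0.318 = 4.2 |

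*Cut at the 75th percentile* (0.446), p = 50%. Below the cut d = −0.271, effect = 8.1 − 8.1 × 0.229 = 6.2. Above it d = −0.120, effect = 8.1 − 8.1 × 0.380 = 5.0. A uniform effect now looks larger in families with less distress.

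Such a cut is plausible. Section 9.6.1.2 gives a threshold of 5 for mild symptoms on both parent scales. From the Table 7 means that lies (5 − 2.95)/3.4 = 0.60 SD above the mean for GAD-7 and (5 − 3.3)/3.7 = 0.46 SD above for PHQ-8. The plan names no cut-point.

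Simulation of the same model with 4,000,000 subjects agreed, and baseline splits gave about 8.1 on both sides of either cut.

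**4. A different causal structure.** Suppose instead that nothing is mediated, but distress and HRQOL share causes. Assumed: baseline distress correlates 0.5 with 3-month distress and −0.4 with HRQOL. With 2,000,000 subjects per scenario, median splits on the 3-month value gave:

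| PRISM lowers distress by | Residual correlation 0 | 0.3 | 0.5 |
|---|---|---|---|
| 0.5 SD | 7.0 | 5.7 | 4.9 |
| 0.25 SD | 7.6 | 6.9 | 6.5 |
| 0 | 8.1 | 8.1 | 8.1 |

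Here a linear regression with a treatment-by-modifier term showed that term at about 0. In that form the distortion lies in the size of the effects and creates no false interaction.

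**The case against.** Four points can be made for the plan, and each has some force.

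*The wording is open.* The word concurrent qualifies parent distress only. A reader might infer that symptom distress is also to be taken at 3 months; the text does not say so, and a baseline MSAS is equally available. Even for parents, concurrent could mean surveyed alongside the patient, since Section 4.1 puts both on the same schedule. That reading is possible but less natural: the sentence concerns a 12-week outcome, and the plan writes baseline elsewhere when it means baseline.

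*The bias is conditional.* A hypothesis that PRISM lowers distress is not evidence that it does, and Section 2.1.3 calls the link between PRISM and parent outcomes unknown. This stands: without an effect on the modifier there is no such bias.

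*False modification is not inevitable.* Median splits and a linear interaction term showed none in the settings above. It arose with the off-median cut, which the plan leaves open.

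*The analyses only explore.* This also stands, and limits the consequence. It does not make a post-randomization subgroup interpretable.

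**Conclusion.** The point holds in conditional form. On its natural reading, Section 11.5.2 conditions on a variable that the plan itself treats as an outcome of PRISM, and it leaves the timing of the other two modifiers open. If post-randomization values are used and PRISM changes them, subgroup effects are distorted: from 8.1 to about 6.8 to 4.2 at a median split in the mediation illustration, and to 7.6 to 4.9 in the shared-cause one. The 0.5 SD shift matches the Table 7 detectable difference for parents. Its use for symptom distress, the mediated shares, the correlations, the normal distributions and the cut-points are all assumptions, so the figures show scale and are not predictions.

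A reader might go further and infer that the subgroup results are bound to be biased, or that the trial's main conclusion is at risk. The documents support neither: the timing is partly unstated, the effect on the modifiers is unknown, and the primary comparison, sample size and power do not use these variables.

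**What to change.** Reword the modifiers in the subgroup sentence of Section 11.5.2 as: baseline medical covariates, baseline symptom distress (MSAS) and baseline parent distress (GAD-7, PHQ-8), each tested as a treatment-by-baseline interaction.

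Limit the parent-distress analysis to participants whose parent survey was completed before randomization. It should not be assumed that all were: parent surveys are optional (note under Section 3.2.3), and Sections 9.2.1 and 9.3.2.2 tie randomization to baseline surveys without clearly requiring the parent's.

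Label any use of 3-month distress as exploratory mediation or association, not effect modification. The mediation analyses in Section 11.5.3.4 do not already cover this; the mediator given there is activation, not symptom or parent distress.

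The cost is a few sentences. No new data collection is needed and no planned number changes. The parent-distress analysis may lose some participants whose parent survey is absent or late.

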### 11.5.3 Secondary Outcomes

**11.5.3.1** The goal for parent outcomes is to evaluate the effect of the intervention on *parent psychological distress* and HRQOL. Mean total scores from each parent instrument at 12 weeks will be the secondary outcomes of interest. We will model distress and HRQOL separately and follow a similar approach to the analyses for continuous outcome measures in Aim 1. As sex and baseline patient HRQOL may be predictors of these outcomes, each will be included if imbalanced between arms.

**11.5.3.2** To compare patient and caregiver *activation*, we will measure patterns in multiple domains: AYA- and parent-reported Decision-Making Involvement Scores, AYA participation in goals of care conversations, and formal palliative care service utilization including documented referrals for hospice and charted decisions to limit resuscitative efforts. For all outcomes, results between trial groups will be compared using analysis of variance with trial group as the factor of interest. We will explore whether change in activation scores are correlated within families and/or modified by parent/child characteristics (sex, psychological distress scores, cancer/tumor-type, among others) using ordinal logistic regression models with cumulative logits, where change activation level is categorized as negative, null, or positive.

**11.5.3.3 Exploratory analyses** will evaluate prospective and longitudinal survey and clinical data beyond month 3 (primary endpoint) at months 6, 9, and 12 of the study. Comparisons between groups will still use an intention to treat approach as described above. Additionally, we will explore the relationship between biomedical variables and patient reported anxiety and depression through a combination of paired and unpaired t-tests, chi-squared (or Fisher's exact) tests, and linear and logistics regression. HRV will be measured in 24-hour increments using both time and frequency domain parameters as established by the international Cardiology task force

guidelines. Means and standard deviations will be compared to published normative data in adolescents.

**11.5.3.4 Additional analyses** will include process evaluations that include: (a) intervention fidelity; (b) satisfaction queries; and (c) mediation analyses to evaluate relationships between PRISM, family activation, and outcomes. For example, the intervention effect on parent outcomes may be mediated by parent activation. If we find a positive intervention effect on parent psychological distress, we will explore activation mediation using the counterfactual framework with indirect mediation effects computed through G-estimation and incorporating confounders of the mediator-outcome association. Finally, we will conduct a planned interim analysis for data-safety monitoring purposes when half of AYA participants have reached the primary endpoint (see Human Subjects).

**11.5.3.5 Multiple comparisons.** Multiple comparisons are a concern since we are collecting multiple measures from both patients and caregivers and are interested in several hypotheses. We minimize this problem by specifying a limited number of main hypotheses for each aim. False Discovery Rate criterion will be used to correct for multiple testing in analyses that are not pre-specified. Likewise, in manuscripts and presentations, we will report the number of tests performed and interpret results within this context.

**11.5.3.6 Considerations regarding missing data.** Effective data collection at scheduled times will be monitored and attrition minimized as described below. While our goal will be to minimize missing data, data may still be missing due to patients/families skipping individual items, omissions in medical records, lack of follow-up, medical complications, or death. We will quantify the amount of missing data, evaluate the association of participant characteristics with missing data, and minimize bias and increase efficiency in the associations of interest by applying appropriate methods to account for missing data. For example, where missing at random (MAR) is a plausible assumption, we will use multiple imputation or inverse probability weighting, depending on the statistical model being considered. For missing not at random (MNAR), we will use sensitivity analyses. In all cases, we will assess the robustness of estimates due to assumptions.

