## 8.0 Study Endpoints

**8.1.1 Primary Endpoint: 3-month follow-up of last AYA participant including patient-reported outcome survey completion.**

**8.1.2 Secondary Endpoints:**

8.1.2.1 3-month follow-up of last parent participant including parent-reported outcome survey completion.

8.1.2.2 3-month data collection of “palliative care activation” measures, including surveys, medical record data extraction.

8.1.2.3 12-month follow-up of last participant for exploratory cohort.

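### Section 11.5.3.2 compares 12-week Decision-Making Involvement scores without the baseline score that is already collected; the test is valid but gives up some precision

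*Combined protocol and SAP*

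**What the plan says.** Section 1.2.3.5.1 lists "AYA- and parent- perceptions of AYA involvement in Decision-Making" as the first activation outcome under the secondary aims. Section 8.1.2.2 sets 3-month collection of activation "measures, including surveys, medical record data extraction" as a secondary endpoint.

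The group comparison is in 11.5.3.2: "For all outcomes, results between trial groups will be compared using analysis of variance with trial group as the factor of interest". The section uses baseline activation data in one place only, an exploratory ordinal model: "We will explore whether change in activation scores are correlated within families".

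Three other parts of the analysis plan bear on the baseline score.

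- Section 11.5.1 adjusts every analysis for site and age. It admits other baseline variables only where the arms are clearly out of balance.
- Section 11.5.2, on the primary outcome, says "we will control for baseline HRQOL as a covariate in the regression". It then carries the same analysis over to the PedsQL subscales, "the cancer-specific module, and secondary outcomes included in AYA surveys".
- Section 11.5.3.1, on parent outcomes, says "Mean total scores from each parent instrument at 12 weeks will be the secondary outcomes of interest", and then: "We will model distress and HRQOL separately and follow a similar approach to the analyses for continuous outcome measures in Aim 1".

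On data collection, 9.6.1.3.1 puts the scale in both the full and the abbreviated RCT surveys, for AYAs and parents. Section 9.6 gives the full survey at baseline and week 12. Section 4.1 has parents surveyed at the same time points as AYAs, and 9.2.1 randomizes patients only once baseline surveys are complete.

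**The concern.** The pre-treatment value of this outcome is scheduled for both respondents, and the plan already needs it for the exploratory change analysis. Yet it enters the main between-arm comparison only if it happens to be imbalanced, a condition given no threshold. In a randomized comparison, the baseline value of the same measure is usually the most useful covariate available, and leaving it out widens the confidence interval whenever it predicts the 12-week score.

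There is also a smaller question of clarity. The AYA-reported score is a secondary outcome and sits in the AYA survey, so the carry-over phrase in 11.5.2 could be taken to reach it. That would give a baseline-adjusted regression where 11.5.3.2 gives an ANOVA. For the parent-reported score, the first quoted sentence of 11.5.3.1 is broad, but the modelling sentence that follows is confined to distress and HRQOL.

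At stake are the precision of a secondary comparison that carries a directional hypothesis (1.2.3.5.2), and a reader's certainty about which model produced the result.

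**Working it through.** **Step 1. Is the baseline score available?** Yes, by schedule. Sections 9.6.1.3.1, 9.6 and 4.1 together place the scale at baseline and week 12 for AYAs and parents. For AYAs, 9.2.1 puts the baseline survey before randomization. Parent baseline surveys are scheduled but are not stated as a condition of randomization.

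**Step 2. Reproduce the plan's own figure.** Table 7 gives no row for this scale; the nearest is PedsQL generic: SD 17.2, 72 per arm, 80% power, 5% type I error (taken as two-sided), detectable difference 8.1.

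- Normal approximation: difference = SD × √(2/n) × (1.960 + 0.842) = 17.2 × √(2/72) × 2.802 = 8.03.
- Noncentral t: 8.09, which rounds to the stated 8.1.
- Attrition: 195 × 0.74 = 144.3, matching 144 evaluable.

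The stated figures match a two-sample comparison with no gain from a baseline covariate. In SD units the effect is 8.1/17.2 = 0.47.

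**Step 3. Effect of adding the baseline score.** With baseline-to-week-12 correlation r, the residual SD is multiplied by √(1 − r²), and one degree of freedom is spent. Power comes from a noncentral t with noncentrality [d/√(1 − r²)] × √(n/2) and 2n − 3 degrees of freedom (2n − 2 without the baseline score).

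Inputs: d = 0.47 (borrowed from PedsQL), n = 72 per arm for AYAs, n = 64 per arm for parents (the planned minimum in 11.3.1.3), and r from 0.1 to 0.5 (assumed).

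| Model | Power, 72/arm | Detectable difference, 72/arm | Power, 64/arm | Detectable difference, 64/arm | CI narrower by |
|---|---|---|---|---|---|
| No baseline | 80.0% | 0.470 SD | 75.1% | 0.499 SD | – |
| r = 0.1 | 80.4% | 0.468 SD | 75.5% | 0.497 SD | 0.5% |
| r = 0.2 | 81.6% | 0.461 SD | 76.8% | 0.489 SD | 2.0% |
| r = 0.3 | 83.5% | 0.448 SD | 79.0% | 0.476 SD | 4.6% |
| r = 0.5 | 89.9% | 0.407 SD | 86.1% | 0.432 SD | 13.4% |

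Detectable differences are at 80% power. The last column is 1 − √(1 − r²). Allowing degrees of freedom for age and three site terms changes the powers by at most 0.0003.

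**Step 4. Check by simulation.** Age and site were in both models, with 20,000 trials per setting. At r = 0.3 and 72 per arm, power was 79.8% without and 83.1% with the baseline score; at r = 0.5 it was 80.3% and 90.0%. At r = 0 the baseline term cost 0.4 point at both sizes (79.7% to 79.3% at 72 per arm, 75.3% to 74.9% at 64 per arm). Under the null, both models rejected in 4.5% to 5.7% of 8,000 trials per setting.

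**Step 5. Where in the range is r likely to lie?** Section 9.6.1.3.1 reports alpha of 0.68 to 0.71 and has each respondent think of one important conversation in the past month, so the two administrations may concern different conversations. If alpha is taken as reliability, observed r = alpha × true-score stability. Then r = 0.3 needs stability of 0.3/0.71 = 0.42 to 0.3/0.68 = 0.44, and r = 0.5 needs 0.5/0.71 = 0.70 to 0.5/0.68 = 0.74. The lower part of the table is therefore the more plausible.

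**The case against.** The strongest reply is that the plan is already complete for this scale. Table 5 assigns it to Aim 3, separate from the AYA outcomes of Aim 1. Section 1.2.3.3.1 lists the AYA patient-reported outcomes without it, and 11.5.3.1 refers to Aim 1 in a way that treats 11.5.2 as the Aim 1 section. Section 11.5.3.2 names the scale and states its model for all activation outcomes. A specific instruction normally governs over a general carry-over phrase.

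That stands. A reader might infer from 11.5.2 that the plan contradicts itself on the AYA score. The documents allow that reading but do not support it well: the aim structure favours 11.5.3.2. For the parent score there is no contradiction, only the absence of a baseline term.

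It is also fair to say that 11.5.2 justifies baseline adjustment by the dependence of change on initial HRQOL, and claims no such dependence for this scale. That lowers the expected gain but does not remove the case for the covariate, since the cost if the correlation is nil is so small.

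A reader might further infer that the comparison is unadjusted, biased or prone to false positives. It is not. Section 11.5.1 adds age and site; randomization makes the comparison unbiased in expectation without the baseline score; and the simulated null rejection rates are close to 5% for both models. Section 9.2.1 also blinds the analysts to allocation, which limits any selective choice of model.

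**Conclusion.** The point holds as a minor, nearly free improvement in efficiency, not as an error or an established conflict. The baseline score is collected, but the main comparison leaves it out unless imbalance happens to bring it in.

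Under the assumed 0.47 SD effect, the gain is 0.4 to 3.5 points of power at 72 per arm for r of 0.1 to 0.3, rising to about 10 points at r = 0.5. At 64 per arm the corresponding gains are 0.4 to 3.9 points and 11 points. The likely gain is small to moderate.

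The effect and the correlation are assumptions, and no SD is given for this scale. Because it has no row in Table 7, no stated power claim is undermined. The primary outcome and the sample size are untouched. Confidence is medium.

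**What to change.** In 11.5.3.2, state that AYA- and parent-reported 12-week Decision-Making Involvement scores (by subscale, if scored that way) are compared between arms by ANCOVA, with the same respondent's baseline score as a covariate and the age and site terms that 11.5.1 already requires. Add that this governs over the carry-over phrase in 11.5.2 for this scale. Missing parent baselines can be handled under the missing-data provisions of 11.5.3.6.

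The cost is one or two sentences and no new data. If baseline and week 12 prove uncorrelated, the loss is about 0.3 to 0.4 point of power.
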